2 INTRODUCTION

Multifocal contact lenses (MF) provide correction for vision at near as well as in the distance. This segment of the contact lens market has been slowly growing as more products become available.

CooperVision is interested in comparing the performance of two of their newly developed daily disposable contact lenses, clariti 1day MF 2-ADD design (CONTROL lens) and clariti 1day MF 3-ADD design (TEST lens) contact lenses. Of particular interest is the comparison of subjective response related to distance vision. Achieving acceptable distance vision is one of the important factors for successful multifocal lens wear.

3 OBJECTIVES

The objective of the study is to adapt existing multifocal soft lens wearers to a CONTROL lens (clariti 1day MF 2-ADD design) for 2 weeks and then evaluate the success of switching them to the TEST lens (clariti 1day MF 3-ADD design), with a review after 2 weeks.

The primary outcome variable for this study is:

- Subjective ratings of 'comfort on insertion', using a 0-10 scale, in 0.5 steps, collected using at-home ratings on Day 1, the day after the lens dispense visit.

4 HYPOTHESIS

The null hypothesis is that there will be no difference between the at-home subjective ratings of 'comfort on insertion', collected on Day 1 for CONTROL lens compared to TEST lens.

5 MATERIALS AND METHODS

5.1 STUDY DESIGN

5.1.1 OVERALL DESIGN

This is a prospective, crossover, bilateral daily wear and subject masked dispensing study conducted at several clinical practice sites in the United States. The habitual contact lenses will not be optimized. There will be no randomization of the study lenses, participants will wear the CONTROL for the first wear period and the TEST for the second wear period. Participants will wear each study lens for 3-7 days and then attend for a prescription optimization visit. After this optimization visit they will wear each study lens for a 2-week period. During the 2-week wear period, participants will record their subjective lens-wear experience remotely on three different days (days 1, 6 and 13), using paper diaries.

5.1.2 RANDOMIZATION

There will be no randomization, participants will wear CONTROL for the first wear period and TEST for the second period.

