5.3.1 SAMPLE SIZE CALCULATION

The sample size was calculated using data of 'lens comfort at insertion' collected in a previous study involving clariti 1day (CooperVision, data on file). In that study a 0-100 scale was used, not

the 0-10 used in this study. A difference of 7 on that 0-100 scale was targeted, which would be 0.7 on the 0-10 scale. However, in this study, a 0-10 scale will be used with 0.5 steps, and analysis is anticipated to be non-parametric, which relies on medians not means, thus a difference between medians can only be as low as 0.5.

Using the 0-100 scale data described above for 'lens comfort at insertion', the data showed a standard deviation of paired differences of 16.5. With an alpha 0.05 in a paired difference test, and power of 84%, a minimum sample size of 51 participants is recommended in order to detect a statistical difference between study lenses.

To account for dropout, up to 60 participants may be randomized and dispensed with study product in total, with the target of at least 51 completing the study.

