5.3.2 NUMBER OF PARTICIPANTS

Participants will be recruited using site record and, databases using an email script, where consent for contact about research has been provided. There will also be general advertising materials (eg. posters, social media posts) and all these, including email scripts, will be approved by the ethics review board. All initial individual-targeted recruitment activities, such as any direct mailing of recruitment scripts, will be conducted by practice staff that are not directly involved in conducting the research. This separation will reduce any undue influence of the optometrist-patient relationship. This process will also eliminate opportunity for the investigator to access personal health information before any consent for disclosure is provided by the potential participant.

It is anticipated that up to 80 potential participants may attend a Screening visit and up to 60 participants may be dispensed with study products, with a target of 51 completing the study.

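### With CONTROL always worn before TEST, the Day 1 paired test measures the change on switching; Section 5.3.1, and a lens-versus-lens reading of Section 4, claim more than that

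*Combined protocol and SAP*

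**What the plan says.** The order is fixed and disclosed. Section 5.1.2: "There will be no randomization, participants will wear CONTROL for the first wear period and TEST for the second period". Section 5.1.1 says the same, but labels the design a crossover: "This is a prospective, crossover, bilateral daily wear and subject masked dispensing study".

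The protocol describes its question in two ways.

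- **Switching.** Section 3 sets out to adapt multifocal wearers to CONTROL and then to "evaluate the success of switching them to the TEST lens".
- **Lens against lens.** Section 4 states the null as "no difference between the at-home subjective ratings of 'comfort on insertion', collected on Day 1 for CONTROL lens compared to TEST lens". Section 5.3.1 sizes the study at 51 participants, with 84% power, "in order to detect a statistical difference between study lenses". As background, Section 2 gives the sponsor's interest as "comparing the performance of two of their newly developed daily disposable contact lenses".

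Section 5.3.1 also says "up to 60 participants may be randomized and dispensed with study product in total". Section 5.3.2 gives the same count without that word: "up to 60 participants may be dispensed with study products".

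The visible text does not state that lens and period are confounded, and it sets no limit on what may be concluded about the lenses.

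**The concern.** In a crossover with two sequences, half the participants meet the lenses in each order, so a period effect can be estimated and removed. Here there is one sequence. Anything that shifts ratings between the first and second wear period, such as adaptation, passage of time or practice with the diary, enters the CONTROL-to-TEST difference in full.

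What is at stake is the conclusion. A significant result supports the statement that ratings changed after wearers moved from CONTROL to TEST. It does not by itself show that TEST differs from CONTROL, and a null result does not by itself show that the lenses are alike. A report that follows the wording of 5.3.1 would make the lens claim.

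**Working it through.** **1. The plan's own figure.** Inputs from 5.3.1: target difference 7 and SD of paired differences 16.5 on a 0-100 scale, that is 0.7 and 1.65 on the 0-10 scale; alpha 0.05; power 84%; 51 participants. Sidedness is not stated, so I take two-sided.

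- SE = 1.65/√51 = 0.2310
- Noncentrality = 0.7/0.2310 = 3.03, with 50 degrees of freedom and critical t 2.0086
- Power = 84.4% at n = 51 and 83.7% at n = 50

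So 51 is the smallest n that reaches 84%, and the figure reproduces. A one-sided alpha would need only about 39 by the normal approximation. There is no arithmetic error.

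**2. What the paired difference estimates.** For each participant let D = (TEST rating in period 2) − (CONTROL rating in period 1). Then

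E(D) = lens effect + period effect (+ any carryover from CONTROL).

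One sequence gives one mean and at least two unknowns. Only the sum is estimable, whatever test or model is used.

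**3. How far apart the two ratings are.** Day 1 is the day after dispensing (5.5.5), so the gap between the two Day 1 ratings equals the gap from Visit 3 to Visit 7.

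- Visit 3 to Visit 4: 14-16 days (5.5.6)
- Visit 5 to Visit 6: 3-7 days (5.5.8)
- Visits 4 and 5, and Visits 6 and 7, fall on the same day if lenses are on site

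The gap is 14 + 3 = 17 to 16 + 7 = 23 days, and longer if lenses have to be ordered. The TEST rating also follows a scheduled round of diary ratings on days 1, 6 and 13 (5.1.1). Wear in the gap need not be continuous: 5.5.4 allows habitual lenses while optimized lenses are on order, and 5.5.8 carries the Visit 2 procedures over to TEST.

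**4. Illustration.** The documents give no period effect, so the shifts below are assumptions. Two-sided paired t-test, n = 51, SD 1.65:

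| Assumed period shift (0-10 scale) | Significant result, identical lenses | Power, true lens effect 0.7 with the shift opposing it |
|---|---|---|
| 0 | 5.0% | 84.4% |
| 0.1 | 7.1% | 72.1% |
| 0.2 | 13.6% | 56.5% |

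A shift of about 0.15, under a third of one 0.5 rating step, doubles the rate to 10%. The smallest significant mean difference is 2.0086 × 0.2310 = 0.464, whatever its source.

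Section 5.3.1 expects a non-parametric analysis. A signed-rank simulation (20,000 runs per setting; normal differences rounded to 0.5, without the bounds of the 0-10 scale) gives 5.1%, 6.9% and 13.6% in the first column, and 82.9%, 70.5% and 55.1% in the second.

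**The case against.** The other side has good points, and most of them narrow the concern.

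- **The fixed order is deliberate and open.** Section 3 states a switching objective, and 5.1.1 and 5.1.2 both say there is no randomization. This stands. A reader might infer that the design is invalid or must be randomized; the documents do not support that, because the paired test is sound for the question in Section 3.
- **Section 4 can be read literally.** It speaks of ratings collected under each lens, which is what the test examines. This stands too, so the overclaim in Section 4 lies in one reading of it. The wording in 5.3.1 is harder to read that way.
- **Section 2 is background.** A reader might infer that it presents the Day 1 test as a lens comparison. It does not mention Day 1 or insertion comfort, and singles out subjective response on distance vision. It matters only as an interest that the design meets in a limited form.
- **The illustrated rates are not errors for the switching question.** Correct: there a period shift is part of what is tested. A reader might take 7% to 14% as the trial's actual false-positive rate; nothing in the documents supports that.
- **Prior multifocal wear, the 3-7 day run-in on each lens and subject masking may reduce a period effect.** They may, but they do not identify it.
- **A limit may be stated out of sight.** Section 12.1 is redacted, and Section 16 refers to a contract that is not shown. Neither can make the lens effect estimable, but either might restrict interpretation. No overclaiming report text exists in the documents.
- **The word *randomized* in 5.3.1 is a leftover.** A reader might infer a claim of random allocation. Sections 5.1.1 and 5.1.2 openly deny it, and Section 14 uses the word for assigning a study ID. It is clerical and affects neither N nor the analysis.

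**Conclusion.** The concern holds as one of wording and interpretation. The Day 1 paired difference tests the change in rating on switching from CONTROL to TEST, as Section 3 intends, and cannot separate lens from period. The 84% power in 5.3.1 therefore belongs to the change on switching; it is power for a lens difference only if the period effect and carryover are nil. A lens-versus-lens reading of the Section 4 null goes too far for the same reason.

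The identification point needs no numerical assumption. Its practical size cannot be determined from the documents, because the size and direction of any period effect are unknown. The 7% to 14% range rests on assumed shifts of 0.1 to 0.2 points, identical lenses and the planned SD, and applies only if a lens effect is claimed. The correction is worth making because it settles what the trial may conclude and leaves its conduct as it is.

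**What to change.** - **5.3.1:** state the detectable quantity as a change in rating after switching from CONTROL to TEST, in place of a difference between the lenses.
- **Section 4:** state the null as no change in the at-home Day 1 rating of comfort on insertion after switching from CONTROL to TEST.
- **5.1.1:** replace the crossover label with *single-sequence (CONTROL then TEST), within-participant*, and add one sentence: *Because all participants wear CONTROL first, lens and period effects cannot be separated; conclusions are limited to the change on switching.*
- **Clerical:** delete *randomized* in 5.3.1, to match 5.1.2 and 5.3.2.

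The order, visits, test and target of 51 completers stay the same, and nothing needs recomputing. The cost is that the lens-comparison interest in Section 2 is openly narrowed, which the sponsor has to accept.

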5.1.3 MASKING

Subjects will be masked to the order they wear the study contact lenses in this study. All dispensed contact lens blister packs will have a masking label affixed to the foil which will obscure the lens identifying information.

5.2 INVESTIGATIONAL SITES

5.2.1 NUMBER OF SITES

This study will be conducted at several optometry practice sites in the United States. The site details will be included in the study report.

5.2.2 INVESTIGATOR RECRUITMENT

The principal investigator at each site will be required to fulfil the following criteria:

- Is a licensed eye care professional with at least two years of contact lens fitting experience.
- Can demonstrate training in Good Clinical Practice (GCP) by the already trained principal investigator.
- Accepts responsibility for the conduct of the study at their site.
- Has in-office email and document scanning capabilities.
- Will scan and send all study visit documents to CORE, ideally the same day* as the visit or at most within 2 days of the study visit.
- Is willing to follow the study protocol and to co-operate with the study monitors at CORE.

* Study documents are required as soon as possible because this allows for prompt lens ordering and timely data review, query and entry.

5.3 STUDY POPULATION

[figure not shown]
5.3.1 SAMPLE SIZE CALCULATION

The sample size was calculated using data of 'lens comfort at insertion' collected in a previous study involving clariti 1day (CooperVision, data on file). In that study a 0-100 scale was used, not

the 0-10 used in this study. A difference of 7 on that 0-100 scale was targeted, which would be 0.7 on the 0-10 scale. However, in this study, a 0-10 scale will be used with 0.5 steps, and analysis is anticipated to be non-parametric, which relies on medians not means, thus a difference between medians can only be as low as 0.5.

Using the 0-100 scale data described above for 'lens comfort at insertion', the data showed a standard deviation of paired differences of 16.5. With an alpha 0.05 in a paired difference test, and power of 84%, a minimum sample size of 51 participants is recommended in order to detect a statistical difference between study lenses.

To account for dropout, up to 60 participants may be randomized and dispensed with study product in total, with the target of at least 51 completing the study.

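### Is the 84% power in section 5.3.1 left without a difference or a test, and does half-point scoring limit the analysis to differences of 0.5?

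*Combined protocol and SAP*

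**What the plan says.** Section 5.3.1 sizes the study from an earlier comfort study scored 0-100. The target is explicit: "A difference of 7 on that 0-100 scale was targeted, which would be 0.7 on the 0-10 scale". A remark on the present scale follows: because ratings move in half points, "analysis is anticipated to be non-parametric, which relies on medians not means, thus a difference between medians can only be as low as 0.5". The next paragraph goes back to the 0-100 data, where "the data showed a standard deviation of paired differences of 16.5", and concludes: "With an alpha 0.05 in a paired difference test, and power of 84%, a minimum sample size of 51 participants is recommended". That last sentence does not restate the difference, does not say one- or two-sided, and calls the test only a paired difference test.

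Two other places bear on it. Section 4 opens: "The null hypothesis is that there will be no difference between the at-home subjective ratings". Section 5.3.2 sets the ceiling on numbers: "up to 60 participants may be dispensed with study products, with a target of 51 completing the study".

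No readable section names the primary test. Section 12.1 is blacked out, including its heading in the table of contents, and the readable text of section 12 starts at 12.2, so a test may be named there.

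**The concern.** The order of the sentences invites a misreading. The target of 0.7 comes first, the remark about 0.5 seems to qualify it, and the power figure follows with no difference attached. Someone who thinks 0.5 has replaced 0.7 would credit the study with 84% power for a half-point difference and read a null result accordingly.

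The remark is also weak statistics. It argues from a non-parametric analysis to a comparison of medians, and from there to a smallest difference of 0.5. The usual paired non-parametric test, the Wilcoxon signed-rank test, ranks within-participant differences and does not compare two sample medians. Finally, the power figure seems to come from a parametric calculation while the analysis is expected to be non-parametric, so the 84% might not apply to the test that is run.

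**Working it through.** **Inputs (section 5.3.1).** Difference 7 and SD of paired differences 16.5 on 0-100, which are 0.7 and 1.65 on 0-10; alpha 0.05; power 84%; n = 51. Carrying the SD over to the new scale by dividing by 10 is the plan's implicit assumption.

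**1. Reproduce the plan's figure.** For a two-sided paired t-test the noncentrality is (difference/SD) × √n = (0.7/1.65) × √51 = 0.4242 × 7.141 = 3.03, with 50 degrees of freedom and critical value 2.009.

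| Difference | Sides | n | Power | Smallest n for 84% |
|---|---|---|---|---|
| 0.7 | two | 50 | 83.7% | |
| 0.7 | two | 51 | 84.4% | 51 |
| 0.7 | one | 51 | 91.0% | 41 |
| 0.5 | two | 51 | about 56% | 97 |
| 0.5 | one | 51 | 68.8% | 78 |

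Of these combinations, only 0.7 two-sided returns both stated figures. At 0.5 the noncentrality is (0.5/1.65) × 7.141 = 2.16, and the 97 needed is well above the 60 who may be dispensed.

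**2. Replace the t-test with a signed-rank test.** Its asymptotic efficiency relative to the t-test for normal differences is 3/π = 0.955, so 51 pairs act like 51 × 0.955 = 48.7.

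- Power at 0.7 is 82.7% by this route. Simulations with differences rounded to half points gave 82.5% (20,000 runs) and 83.3% (6,000 runs).
- Power at 0.5 is about 55%.
- About 53 completers (simulation) or 54 (efficiency) restore 84%, within the 60 allowed.

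**3. Does half-point scoring cost power?** Rounding to steps of 0.5 adds about 0.5²/12 = 0.021 to a variance of 1.65² = 2.7225, which moves the SD from 1.65 to about 1.656. Simulated signed-rank power at 0.7 was 82.2% unrounded and 82.5% rounded, a gap within simulation error.

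**4. Is there a floor at 0.5?** Take 51 paired differences: 26 of zero, 20 of +0.5 and 5 of −0.5. The median difference is 0 and the mean is (10 − 2.5)/51 = 0.15. Dropping the zeros leaves 25 tied values, each with rank 13.

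- Positive rank sum: 20 × 13 = 260
- Expected under the null: 25 × 13/2 = 162.5
- SD: √(25 × 13²/4) = 32.5
- z = (260 − 162.5)/32.5 = 3.0, two-sided p = 0.003

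So a paired rank test can detect a shift well below half a point. The plan's sentence holds only in a narrow sense. With an odd number such as 51, each lens's sample median lies on the half-point grid, so two unequal medians differ by at least 0.5. With an even number a median can fall between grid points: ratings of 8.0 and 8.5 give 8.25.

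**The case for a change.** The strongest case for a change is that a power statement should carry its own difference, test and sidedness. Here the reader must work backwards to find them, and the last difference mentioned before the 84% is the wrong one. The gap between 84% and about 55% is large, and rewording would cost two or three sentences.

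The drafting criticism stands. It is softened by three things. The calculation paragraph returns to the 0-100 data, and on that scale the only difference stated is 7. The null of no difference in section 4 points to a two-sided test. And the plan never claims power at 0.5, nor equivalence of the lenses.

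It could also be argued that the plan should warn that a null result cannot exclude a half-point difference. As a general statement that would be wrong, because it depends on the confidence interval obtained. With 51 completers and the planning SD, the 95% half-width is 2.009 × 1.65/√51 = 0.46. An estimate within about 0.04 of zero would exclude half a point in both directions; a null result further from zero would exclude it in one direction only. The interval in the report will show which.

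The missing test name cannot be pressed, since section 12.1 cannot be read.

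**Conclusion.** The concern does not call for a change. The stated target, SD, alpha, power and sample size agree with one another: 84% belongs to a 0.7 difference under a two-sided paired t-test (84.4% at 51). Moving to a signed-rank test costs about 1 to 2 points if the differences are roughly normal, and the 60 who may be dispensed cover the two or three extra completers that would restore 84%.

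What remains is a power sentence that does not repeat its inputs and an aside about medians that is poor reasoning but feeds into no calculation. An analyst will attach the 84% to the only target that yields it. Clearer wording would alter neither the sample size, nor the analysis, nor how the result is read.

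This rests on the SD of 1.65 carrying over from the earlier study and on the shape of the differences, which the documents do not give. Under assumed skewed shapes, signed-rank power at 51 ran from 77% to 89% at 0.7 and from 41% to 69% at 0.5. That is ordinary planning uncertainty, and rewording section 5.3.1 would not reduce it.

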5.3.2 NUMBER OF PARTICIPANTS

Participants will be recruited using site record and, databases using an email script, where consent for contact about research has been provided. There will also be general advertising materials (eg. posters, social media posts) and all these, including email scripts, will be approved by the ethics review board. All initial individual-targeted recruitment activities, such as any direct mailing of recruitment scripts, will be conducted by practice staff that are not directly involved in conducting the research. This separation will reduce any undue influence of the optometrist-patient relationship. This process will also eliminate opportunity for the investigator to access personal health information before any consent for disclosure is provided by the potential participant.

It is anticipated that up to 80 potential participants may attend a Screening visit and up to 60 participants may be dispensed with study products, with a target of 51 completing the study.

5.3.3 INCLUSION AND EXCLUSION CRITERIA

A person is eligible for inclusion in the study if he/she:

1. Is at least 42 years of age and has full legal capacity to volunteer;
2. Has read and signed an information consent letter;
3. Self reports having a full eye examination in the previous two years;
4. Anticipates being able to wear the study lenses for at least 8 hours a day, 5 days a week;
5. Is willing and able to follow instructions and maintain the appointment schedule;
6. Habitually wears multifocal soft contact lenses, for the past 3 months minimum;
7. Has refractive astigmatism no higher than -0.75DC;
8. Is presbyopic and requires a reading addition of at least +0.75D and no more than +2.50D;
9. Can be fit and achieve binocular distance vision of at least 20/30 Snellen (or +0.20 logMAR) which participants also deem to be 'acceptable', with the available study lens parameters (powers +4.00 to -6.00DS) (see Table 1).

A person will be excluded from the study if he/she:

1. Is participating in any concurrent clinical or research study;
2. Has any known active* ocular disease and/or infection that contraindicates contact lens wear;

3. Has a systemic condition that in the opinion of the investigator may affect a study outcome variable;
4. Is using any systemic or topical medications that in the opinion of the investigator may affect contact lens wear or a study outcome variable;
5. Has known sensitivity to the diagnostic sodium fluorescein used in the study;
6. Self-reports as pregnant, lactating or planning a pregnancy at the time of enrolment;
7. Has undergone refractive error surgery or intraocular surgery.

* For the purposes of this study, active ocular disease is defined as infection or inflammation which requires therapeutic treatment. Mild (i.e. not considered clinically relevant) lid abnormalities (blepharitis, meibomian gland dysfunction, papillae), corneal and conjunctival staining and dry eye are not considered active ocular disease. Neovascularization and corneal scars are the result of previous hypoxia, infection or inflammation and are therefore not active.

Age ≥ 42 years is an inclusion criterion because presbyopia is unlikely in persons aged <42 years and, if present, may not be due solely to presbyopic changes representative of the wider population.

Pregnant and lactating women are not being excluded from the study due to safety concerns but due to fluctuations in refractive error, accommodation and/ or visual acuity that occur secondary to systemic hormonal changes. It has further been shown that pregnancy could impact tear production, which could impact dry eye symptoms. Such fluctuations could affect data, thereby negatively affecting study data integrity.

